6.6.4 Disability Warranting Dopaminergic Therapy

Treatment differences in time to disability warranting dopaminergic therapy during period 1 will be tested by a Kaplan-Meier logrank test with a two-sided alpha = 0.05. Participants lost to follow-up will be censored. Note that subjects will continue to be followed even if they discontinue study drug.

The following secondary analyses of time to disability warranting dopaminergic therapy will be pursued:

- Subjects lost to follow-up will be classified as initiating dopaminergic therapy at the time of their withdrawal.
- Cox regression will be used to compare treatments with adjustment for baseline modified Schwab and England ADL score.

6.6.5 Combined Function and Treatment

A rank-based test of a single outcome combining function as measured by change in MDS-UPDRS I-III total scores and time to disability warranting dopaminergic therapy will be constructed paralleling the Combined Assessment of Function and Survival (CAFS) score methodology developed for ALS.¹⁷ MDS-UPDRS I-III total scores will substitute for ALSFRS-R total scores and time to disability warranting dopaminergic therapy will substitute for time to mortality. The test consists of calculating a rank-sum score for each individual relative to pairwise comparisons with all other subjects. Subjects are ranked according to time to disability warranting dopaminergic therapy when that is observed for both members of a pair or when one is censored after the observed event time for the other. Pairs that cannot be ranked by time to disability warranting dopaminergic therapy are ranked by absolute change from baseline in MDS-UPDRS I-III total score at the maximum follow-up time at which both subjects have an observation. Inference is drawn by calculating a U-statistic from the rank-sum scores.

6.6.6 Subgroup Analyses

The following subgroups will be considered: sex, race (classified as Asian, Black or African American, Caucasian, or other, including multiracial; or as Caucasian vs. non-Caucasian if fewer than 10% of our sample is non-Caucasian), ethnicity (classified as Hispanic or Latino vs. non-Hispanic), use of MAO-B inhibitors at baseline, and age (both categorized as <65 years vs. \geq 65 years and continuous). For each subgroup, the potential for differential benefit from serum urate elevation will be tested by including subgroup, subgroup x time, and subgroup x time x treatment interaction terms into the primary random-slopes model. A significant subgroup x time x treatment 3-way interaction in combination with significantly slower progression among members of a subgroup randomized to serum urate elevation vs. members of the same subgroup randomized to placebo will be taken as evidence of differential benefit. For sex, we will also test for sex-specific effects in selected secondary analyses of efficacy, disability warranting dopaminergic therapy, and symptomatic effects and in safety analyses related to kidney stone risk. For safety analyses, we will also summarize and compare eligible vs. the few ineligible participants in the ST sample.

6.6.7 Pharmacogenetics

The above listed and any subsequently designated genetic variants will be tested as potential modifiers of treatment effect. For each genetic variant, the potential for differential benefit from serum urate elevation will be tested by including genotype, genotype x time, and genotype x time x treatment interaction terms into the primary random-slopes model. A significant genotype x time x treatment 3-way interaction in combination with significantly slower progression among members of a genotype randomized to serum urate elevation vs. participants with the same genotype randomized to placebo will be taken as evidence of differential benefit.

6.6.8 Symptomatic Effects

The presence of symptomatic effects will be tested using a change-point model constructed as a partial linear spline over time with knots at 12 weeks and 24 months. Both fixed and subject-specific random terms for intercept, slope from baseline to 12 weeks, slope from 12 weeks to 24 months, and slope from 24 to 27 months (or from V10-equivalent visit on study drug to SV) will be included. Unstructured covariance will be assumed among the random effects (10 terms). The AT sample will be analyzed. Significantly smaller slopes during wash-out among subjects treated with inosine using one-sided testing at alpha = 0.025 will be interpreted as symptomatic effects. If symptomatic effects are not found on that basis, the absence of symptomatic effects will be judged based on a non-inferiority test using a non-inferiority bound of 6.3 / 3 = 2.1 points/month in the direction of a symptomatic effect and using one-sided testing at alpha = 0.05.

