- Wash-out (Period 2) of 90 ± 7 days, ending ~27 months after enrollment. Three monthly evaluations will be conducted after discontinuation of study drug at V10 (after 24 months of treatment), two by phone (TE1 and TE2 at months 25 and 26, respectively) and the final visit (SV) in person at month 27. The multiple visits will allow for serial assessments of the need for dopaminergic therapy during and after the reversal of any short-term effect of inosine or its withdrawal, as well as for any late adverse effects of the treatment or its withdrawal.

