## 10.5.2 Alternative Analyses

If analysis of the mITT sample does not indicate benefit of randomization to oral inosine, it is still possible that (a) inosine supplementation is beneficial if the mITT estimates are affected by non-compliance or that (b) serum urate elevation itself is protective if achieved. As a key secondary analyses, we will analyze the AT sample, censoring follow-up after discontinuation of study drug. This will provide an estimate of the effectiveness of inosine among those tolerant of supplementation. We will also analyze the AT sample with substitution of mean increase in serum urate from baseline to week 12 in place of randomized treatment assignment to estimate method-effectiveness of serum urate elevation.

We will further evaluate robustness of estimates from our primary analysis in a number of other secondary analyses, including: (a) alternative models for the mean temporal profile, (b) alternative models for handling observations made after loss to follow-up or initiation of dopaminergic therapy, and (c) alternative models for handling covariance among repeated observations. To relax the assumption of linear change over time, a model with visit and visit x treatment terms in place of the time and time x treatment terms will be fit to permit an unstructured temporal profile. Rather than censoring observations after initiation of dopaminergic therapy, we will consider several models that include all MDS-UPDRS

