3.5 Symptomatic Effects

Symptomatic effects will be estimated by changes in motor symptoms (a) during the first 3 months of wash-in at the start of period 1, and (b) during the 3-month wash-out during period 2 or at the end of study drug exposure, if earlier.

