5.15 Blindedness Evaluation

At week 6 and either month 24 (V10), V10-equivalent visit due early study closure, an Unscheduled Visit due to study drug discontinuation, or a Discontinuation of In-person Followup Visit (whichever of the 4 visits comes first), the Site Investigator, Coordinator, and subject will complete a blindedness evaluation in which each is asked to give his/her independent impression of the subject's treatment assignment and the primary and secondary reasons for this opinion. Participants' responses will not be available to the site Investigator or Coordinator when they make their assessments.

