6.2 Analysis Samples

The following analysis samples will be used for testing effectiveness, efficacy, safety, and tolerability endpoints:

- Intent-to-treat (ITT) Sample: Participants who are randomized, classified according to their randomized treatment assignment. Participants determined to have been ineligible prior to randomization, participants who never initiate study drug, and observations made after premature permanent discontinuation of study drug are included in this sample.
- As-treated (AT) Sample: Participants who are eligible, randomized, and take at least one dose of study drug. If a participant permanently discontinues study drug, observations made during period 1 will be censored following the first visit after study drug discontinuation. Separate analyses will classify participants in the AT sample either according to the actual treatment received or according to the average post-baseline serum urate concentration achieved. Participants randomized to inosine who report not taking inosine will be reclassified as placebo participants. Participants randomized to placebo who report taking inosine or whose serum urate during treatment averages 6.5 mg/dL or greater will be reclassified as inosine participants.

• Safety and Tolerability (ST) Sample: Participants who are randomized and take at least one dose of study drug, classified according to the actual treatment received. Participants determined to have been ineligible prior to randomization and observations made after premature permanent discontinuation of study drug are included in this sample.

The primary efficacy analyses will use the ITT sample to best estimate the expected effectiveness of urate-elevating oral inosine supplementation in clinical practice, recognizing that compliance in clinical use may differ from compliance in the clinical trial. Secondary analyses of efficacy outcomes will use the AT sample to best estimate efficacy of inosine supplementation as administered and serum urate elevation as achieved. Analyses of safety and tolerance will use the ST sample.

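### The symptomatic-effect model in SAP 6.6.8 does not apply the SAP 3.5 wash-out definition to participants who stop study drug before V10 or the early-closure visit

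*SAP*

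**What the plan says.** SAP 3.5 measures the second symptomatic effect "during the 3-month wash-out during period 2 or at the end of study drug exposure, if earlier". The wash-out clock therefore follows the individual's drug exposure.

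SAP 6.6.8 specifies a model "constructed as a partial linear spline over time with knots at 12 weeks and 24 months". Its last segment is the "slope from 24 to 27 months (or from V10-equivalent visit on study drug to SV) will be included". On the sample it says "The AT sample will be analyzed".

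SAP 5.15 shows what the equivalent visit is. Among the triggers for the blinding questionnaire it lists a "V10-equivalent visit due early study closure, an Unscheduled Visit due to study drug discontinuation" as separate items. The exception in 6.6.8 thus covers people still on drug when the study closed, not people who had already stopped.

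SAP 6.2 says of an as-treated (AT) participant who permanently discontinues that "observations made during period 1 will be censored following the first visit after study drug discontinuation". It states no censoring for period 2. Protocol 10.5.2 has no period limit ("we will analyze the AT sample, censoring follow-up after discontinuation of study drug"), but SAP section 1 makes the SAP authoritative on analysis.

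Protocol section 9 asks early stoppers to continue in-person visits if willing. Protocol 7.5.2 plans a Safety Visit (SV) even for those who end in-person follow-up.

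**The concern.** The definition and the model cannot both be followed for a participant who stops before V10 or the closure visit. In SURE-PD, urate was back at baseline one month after stopping (Protocol 2.2.3), and maintenance visits are three months apart. The first off-drug visit can therefore hold most or all of the real wash-out, yet the model places it in the on-drug segment. The visit the model does treat as wash-out may come long after the effect was lost.

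The wash-out contrast is part of the evidence on whether slower progression is symptomatic. SAP 6.6.8 uses it both to detect a symptomatic effect and, against a bound of 2.1 points/month, to declare one absent. Early stopping is foreseeable. The protocol provides for permanent discontinuation in several situations. SAP 2.6 reports more kidney stones than expected. SAP 4.6 recognises discontinuations after sites were told of early closeout.

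**Working it through.** **1. The rules applied to one case.** A participant stops at month 10 and stays in clinic follow-up.

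| Visit (month) | Months off drug | Kept under SAP 6.2? | Segment in SAP 6.6.8 |
|---|---|---|---|
| 12 | 2 | Yes, if it counts as the first visit after stopping | 12 weeks to 24 months (on drug) |
| 15 to 24 | 5 to 14 | No | none |
| 27 | 17 | Yes (period 2) | 24 to 27 months (wash-out) |

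**2. The plan's own figures (SAP 3.9 and 6.6.8).**
- SE = sqrt(25/135) × 0.53 = 0.228, given as 0.23 UPDRS units/month.
- Power at 0.65 units/month = Φ(0.65/0.23 − 1.96) = 0.807, against the stated 80%.
- Bound = 6.3/3 = 2.1 points/month.
- SE on the MDS-UPDRS scale = 0.23 × 1.29 = 0.297.

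These reproduce.

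**3. Expected wash-out contrast under the written rules.** Method: expected value of the generalised least-squares estimate, β = (ΣX′S⁻¹X)⁻¹ ΣX′S⁻¹μ. X holds the intercept, the three segment slopes and their treatment differences. S is built from the subject-level components in SAP 3.8 (intercept 77.4, slope 0.230, covariance 2.87, residual 13.9).

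Assumptions: 135 per arm, a 6.3-point symptomatic effect lost evenly over 3 months (true contrast 2.1), everyone attends SV, and no censoring for dopaminergic therapy. The stopping rate is also assumed.

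| Inosine participants stopping early | First off-drug visit scored 0 to 3 months after stopping | Scored a full 3 months after | No off-drug visit scored before SV |
|---|---|---|---|
| 10% | 2.06 | 2.02 | 2.10 |
| 20% | 2.01 | 1.92 | 2.10 |
| 30% | 1.95 | 1.82 | 2.10 |

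Attenuation runs from (2.10 − 2.06)/2.10 = 2% to (2.10 − 1.82)/2.10 = 13%. A variant with separate random slopes per segment gives 1.81, or 14%. At 5% stopping with a full 3-month gap the estimate is 2.06.

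The third column is unbiased because an early stopper has lost the same 6.3 points by month 27 as a completer.

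**4. The same model when inosine truly slows progression.** Take slowing of 6.3/24 = 0.2625 points/month while on drug and no symptomatic effect. A completer is 6.3 points below placebo at both months 24 and 27, so the true wash-out contrast is 0. The month-10 stopper is 0.2625 × 10 = 2.6 points below placebo at month 27, where the on-drug line implies 6.3 at month 24. The gap, 6.3 − 2.6 = 3.7 points, is read as worsening over 3 months. In the full model the contrast becomes about 0.04, 0.09 and 0.14 points/month at 10%, 20% and 30% stopping over months 6 to 18. It is nearly the same when no off-drug visit before SV is scored.

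**5. Effect on the absence test.** At a true effect exactly on the bound, the chance of wrongly declaring absence is Φ((2.1 − e)/0.297 − 1.645), where e is the expected estimate. From a nominal 5% it becomes 7% to 8%, 9% to 15% and 13% to 24% at 10%, 20% and 30% stopping (first and second columns above). A larger wash-out SE would shrink these shifts.

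**6. On-drug slope in this model.** It shifts by at most 0.013 units/month when the true effect is 0.65, and by at most 0.04 when it is 2.1 (both at 30% stopping).

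**7. Remedy checked.** With the knot at each last dose and later visits dropped, the contrast returns to 2.1 in step 3 and to 0 in step 4 at every stopping rate.

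**The case against.** The strongest objection concerns which visit comes first after stopping. Protocol 7.5.1 expects permanent discontinuation to prompt an Unscheduled Visit, normally the day after the final dose, and its procedures do not include the MDS-UPDRS. If that visit counts in the AT rule, the next quarterly score is censored and a purely symptomatic effect is not attenuated. This stands as a possible reading. The SAP does not say whether unscheduled visits count, and the reading does not remove the upward shift in step 4.

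Second, phase 2 retention was high: 95% tolerated treatment at 6 months and 99% completed (Protocol 2.2.3). At 5% stopping the loss is 0.04 against an SE near 0.30. That is fair, and it is why the size is called modest. Phase 3 differs in its trough target and its reported stone rate.

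Third, this is supporting evidence. Protocol 3.2.3 places the wash-out outside the primary analysis, wash-in is assessed separately, and SAP 6.6.9 has its own disease-modification test. That also stands.

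A reader might infer that the model fixes wash-out at month 24 for everyone. It does not: the closure exception moves it for those still on drug. A reader might also infer that the rule systematically hides a symptomatic effect in inosine's favour. Step 4 shows the opposite when progression is truly slowed.

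**Conclusion.** SAP 6.6.8, with the AT rule in 6.2, does not carry out the SAP 3.5 definition for individual early stoppers. That follows from the text and needs no assumption.

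The numerical consequence is modest and conditional. It is an attenuation of about 2% to 14% of a 2.1 points/month symptomatic effect at an assumed 10% to 30% stopping, and none if no off-drug visit before SV is scored. A true slowing gives an upward shift of about 0.04 to 0.14 points/month. The stopping rate, its timing and the speed of loss are assumptions, because the documents give no discontinuation rate. A larger or one-directional bias is not supported. Nor is bias in the primary analysis, which uses the ITT sample and a different model.

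The sign used here follows Protocol 10.5.8, where a larger wash-out slope on inosine signals a symptomatic effect. SAP 6.6.8 words this as a smaller slope and omits wash-in from that sentence. That is a separate discrepancy to settle at the same time.

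**What to change.** In SAP 6.6.8:

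- Put the second knot at each participant's last-dose date, whether that falls at V10, at the V10-equivalent visit, or at permanent discontinuation. This is what 3.5 implies.
- Include scored off-drug visits up to about 3 months after that date in the wash-out segment. Set the window in days so that it contains completers' SV.
- Exclude later observations, including month 27, for participants who stopped earlier.
- State that this rule replaces the AT censoring for this analysis only, and that an unscored Unscheduled Visit does not end a participant's data.

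Leave 6.2 unchanged. Removing its period 1 limit is tempting. But the last dose precedes V10 by a day, so a literal reading could then censor completers' SV data, and every other AT analysis would change.

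Cost: SAP wording and one derived date from the Dose Management Log. Wash-out intervals will vary with quarterly visits, and some added wash-outs will follow stops driven by adverse events, which are not random. Report the contrast also in participants on drug at V10 or V10-equivalent.

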#### 10.5.8 Symptomatic Effects

The presence of symptomatic effects will be tested using a change-point model constructed as a partial linear spline over time with knots at 12 weeks and 24 months. Both fixed and subject-specific random terms for intercept, slope from baseline to 12 weeks, slope from 12 weeks to 24 months, and slope from 24 to 27 months will be included. Unstructured covariance will be assumed among the random effects (10 terms). The AT sample will be analyzed. Significantly smaller slopes during wash-in or larger slopes during wash-out among subjects treated with inosine using one-sided testing at alpha = 0.025 will be interpreted as symptomatic effects. If symptomatic effects are not found on that basis, the absence of symptomatic effects will be judged based on a non-inferiority test using a non-inferiority bound of 6.3 / 3 = 2.1 points/month in the direction of a symptomatic effect and using one-sided testing at alpha = 0.05.

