		1.1 Statistical Software	
		1.2 Summary Statistics	
		1.3 Precision	
		1.4 Administration	
6	5.2	Analysis Samples	.23

6.3 E	Baseline Comparison	24
	ample Size Review	
6.5 II	nterim Analysis	24
6.6 E	fficacy Analysis	25
6.6.	Primary Analysis of the Primary Efficacy Endpoint	25
6.6.2	2 Secondary Analyses of the Primary Efficacy Endpoint	25
6.6.	3 Secondary Efficacy Endpoints	26
6.6.4	4 Disability Warranting Dopaminergic Therapy	26
6.6.5	5 Combined Function and Treatment	26
6.6.0	5 Subgroup Analyses	27
6.6.'	7 Pharmacogenetics	27
6.6.8	3 Symptomatic Effects	27
6.6.9	Disease Modification	
6.6.	10 Multiplicity Adjustments	
6.6.	11 Missing Data	
6.7 S	afety and Tolerability Analysis	
6.7.	I Treatment-emergent Adverse Events	
6.7.2	2 Safety Labs	29
6.7.3	3 Vital Signs	29
6.7.4	4 Additional Continuous Safety Outcomes	29
6.7.:		
6.7.0	5 Alkalinization and Nephrolithiasis	29
6.8 C	Other Analyses	
6.8.		
6.8.2	2 Study Drug Exposure	
6.8.	3 Prior and Concomitant Medication Use	
6.8.4	4 Determinants of change in MDS-UPDRS	
6.8.3	5 Determinants of Early Disability Warranting Dopaminergic Therapy	
6.8.0		
6.8.'	7 Blindedness	
7. Ref	erences	

1. Introduction

This statistical analysis plan (SAP) defines the outcome measures and analysis samples and specifies the planned analyses of data for the SURE-PD3 trial. The SAP supplements the clinical protocol. Please refer to the clinical protocol for details on the rationale for the intervention, eligibility criteria, conduct of the trial, clinical assessments and the timing of their use in the trial, definitions and reporting of adverse events, data management conventions, and regulatory oversight and compliance procedures. In case of discrepancies between the SAP and the clinical protocol concerning matters of data analysis, the SAP is authoritative. On all other matters, the clinical protocol is authoritative.

This SAP specifies data and planned analyses for the main trial. Specification of data and analyses for ancillary studies will be detailed in ancillary SAPs if not covered here.

2. Study Design

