2.1 Overview

This is a phase 3, randomized, two-arm, parallel-group, placebo-controlled, triple-blind, twoperiod, multicenter clinical trial of oral inosine titrated to elevate trough serum urate to 7.1 to 8.0 mg/dL over 24 months with a 3-month wash-out among early Parkinson disease (PD) patients exclusive of those with scans without evidence of dopaminergic deficit (SWEDD). The primary aim is to test the effectiveness of oral inosine dosed to elevate serum urate in slowing or delaying PD progression over 24 months based on rate of change in the Movement Disorders Society Uniform Parkinson's Disease Rating Scale (MDS-UPDRS) Parts I-III total score while participants are not receiving dopaminergic therapy (except possibly a stable dosage of a monoamine oxidase-B [MAO-B] inhibitor at baseline). Randomizations are stratified by site to avoid chance confounding between site characteristics and treatment. The trial is registered at Clinicaltrials.gov/as study NCT02642393 (see https://clinicaltrials.gov/ct2/show/NCT02642393).

The randomized, two-arm, parallel-group design provides an unbiased estimate of effectiveness of oral inosine dosed to elevate serum urate in slowing or delaying PD progression over 24 months during period 1. Tracking symptoms during randomized wash-in and during the non-randomized 3-month wash-out of period 2 will allow estimation of symptomatic effects of serum urate elevation and thereby better evaluate whether any observed effects on PD progression reflect a disease-modifying effect. Note that although suspension of study drug during the wash-out will be unmasked, subjects and staff will remain blinded as to whether this represents a transition off of active treatment or of placebo treatment, and thus treatment comparison of changes during the 3-month wash-out should remain unbiased. The difference in the proportion of subjects requiring dopaminergic therapy after the 3-month wash-out among all those randomized will provide an estimate of disease-modification by serum urate elevation free of any symptomatic effects of study drug.

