3.9 Power for Secondary Outcomes

The trial will have an 80% probability of observing at least one instance of any class of adverse event expected to occur in at least 1.2% of individuals receiving inosine. The trial will have 80% power to detect increased risk of any class of adverse event among subjects receiving inosine if the true risk is two-fold higher and the expected proportion among placebo subjects is at least 14% or if the true risk if four-fold higher and the expected proportion among placebo subjects is at least 3.4%. The trial has 80% probability of declaring serum urate elevation tolerable if the true proportion tolerant under the definition given in Sec. 3.4 at 12 weeks, 12 months, and 24 months is at least 62%.

The estimated SE for symptomatic effects on UPDRS I-III total scores during wash-in between the moderate elevation and placebo arms in the SURE-PD trial was 0.53 units / month. With n = 25 subjects per treatment group in SURE-PD, the expected SE for estimating symptomatic effects in this trial will be roughly sqrt (25/135) * 0.53 = 0.23 units / month. With that SE, the trial would have 80% power to detect symptomatic effects on the order of a difference in slopes during wash-in or wash-out of 0.65 units/month.

The Kaplan-Meier product-limit estimate from the SURE-PD trial of the proportion of placebo subjects requiring dopaminergic therapy by 24 months was 62%. Assuming constant hazard at the same rate among placebo subjects in this trial during period 1 (0 to 24 months) and 8% loss to follow-up prior to determining need for dopaminergic therapy, the trial will have 80% power to detect a hazard ratio of 0.62. Extrapolating to 27 months, we expect a total of 67% of placebo arm subjects to have disability warranting dopaminergic therapy at the end of period 2 (24 to 27 months). The study would have 80% power to detect a difference in the proportion of subjects with disability warranting dopaminergic therapy if 50% or fewer of active arm subjects have progressed by the end of the trial.

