5.1 Movement Disorders Society Unified PD Rating Scale (MDS-UPDRS)

The MDS-UPDRS¹³⁸ will serve as the primary outcome variable of the study and will be conducted at all standard visits beginning with SC2. The MDS-UPDRS was designed by movement disorders experts to address weaknesses of the original UPDRS (e.g., by adding questions on constipation and sialorrhea) while preserving its overall format.

The instrument is divided into four parts:

- Part I (non-motor experiences of daily living), comprising
 - Part IA concerning behaviors that are assessed by the Site Investigator with all pertinent information from participants and caregivers
 - Part IB that is completed by the participant with or without the aid of the caregiver, but independently of the Site Investigator.
- **Part II (motor experiences of daily living)**, designed to be a self-administered questionnaire like Part IB, but similarly can be reviewed by the Site Investigator to ensure completeness and clarity.
- **Part III (motor examination)** has instructions for the rater to give or demonstrate to the participant; it is completed by the clinician rater.
- **Part IV (motor complications)** with instructions for the rater and also instructions to be read to the participant. This part integrates participant-derived information with the rater's clinical observations and judgments and is completed by the rater.

The full MDS-UPDRS has sixty-five items, each assessed on a 5-point Likert scale ranging from 0 to 4 with 0=none, 1=slight, 2=mild, 3=moderate, 4=severe. Total scores for Parts I, II, III, and IV and for Parts I through III collectively are calculated as simple sums of component items with mean imputation by Part if no more than 1, 2, 7, or 0 items is missing for Parts I through IV, respectively.¹⁶ Two additional summary scores will also be constructed: ambulatory capacity (sum of 5 MDS-UPDRS questions: walking and balance [question 2.12], freezing [q. 2.13], gait [q. 3.10], freezing of gait [q. 3.11], and postural stability [q. 3.12]) and patient-reported symptoms (sum of Parts IB and II). Higher scores imply worse symptoms.

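### As supplied, SAP 6.6.8 takes a smaller wash-out slope on inosine as the sign of a symptomatic effect and gives wash-in no presence test; check the source page for a dropped clause before amending it

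*SAP*

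**What the plan says.** Both documents fit the same change-point model to the as-treated sample, with knots at 12 weeks and 24 months. Both use a one-sided presence test at 0.025. If no effect is found, a non-inferiority test of absence follows, against 2.1 points/month at one-sided 0.05. They differ in the presence rule.

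- Protocol 10.5.8: "Significantly smaller slopes during wash-in or larger slopes during wash-out among subjects treated with inosine".
- SAP 6.6.8, as supplied: "Significantly smaller slopes during wash-out among subjects treated with inosine using one-sided testing at alpha = 0.025".

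Other SAP text bears on which is meant:

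- Section 5.1 gives the scale direction: "Higher scores imply worse symptoms".
- Section 2.1 uses both periods: "Tracking symptoms during randomized wash-in and during the non-randomized 3-month wash-out of period 2 will allow estimation of symptomatic effects".
- Section 3.5 lists wash-in first: "a) during the first 3 months of wash-in at the start of period 1".
- Section 3.9 claims "80% power to detect symptomatic effects on the order of a difference in slopes during wash-in or wash-out of 0.65 units/month".
- Section 6.8.7 refers to the change at wash-in as something defined in 6.6.8.
- Section 1 (Introduction) sets precedence: "In case of discrepancies between the SAP and the clinical protocol concerning matters of data analysis, the SAP is authoritative".

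**The concern.** Two things are wrong with the supplied sentence.

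**Direction.** If inosine relieved symptoms, stopping it would let scores rise faster, so the wash-out slope would be larger on inosine than on placebo. The supplied rule looks for the opposite. This conflicts with Protocol 10.5.8 and with the scale direction in SAP 5.1.

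**Wash-in.** The wash-in slope is still estimated in the model, but no presence rule uses it. This conflicts with SAP 2.1, 3.5, 3.9 and 6.8.7, which treat wash-in as part of the assessment. Those sections state no direction, so they bear only on this second fault.

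Because the SAP governs data analysis, the protocol's wording does not automatically correct it. What is at stake is an interpretive claim: SAP 3.1 looks to a delay over two years without symptomatic effects as possible evidence of disease modification, and 6.6.8 is where that absence is judged.

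**Working it through.** **Inputs.** SAP 3.9 takes the phase 2 standard error for wash-in, 0.53 UPDRS units/month with 25 per arm, and scales it to 135 per arm for both wash-in and wash-out. The design effect is 0.65 units/month. The presence test is one-sided at 0.025, critical value 1.96.

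**Step 1: reproduce the plan's figure.**

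- SE = 0.53 × sqrt(25/135) = 0.228, which the SAP rounds to 0.23.
- Detectable difference at 80% power = (1.960 + 0.842) × 0.23 = 0.644, in line with the stated 0.65.
- Power at 0.65 with SE 0.23 is 0.807. The stated figure reproduces, but only when the test points in the protocol's direction.

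**Step 2: apply both rules to a true withdrawal worsening.** Let d = 0.65 be the excess wash-out slope on inosine. With the unrounded SE, d/SE = 0.65/0.228 = 2.85.

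- Protocol rule (larger slope): 1 − Φ(1.96 − 2.85) = 0.81.
- Supplied SAP rule (smaller slope): Φ(−1.96 − 2.85) = 7.6 × 10⁻⁷.
- By symmetry, the supplied rule would label the opposite pattern, d = −0.65, symptomatic with probability 0.81.
- At d = 0 the supplied rule flags 2.5%, its maximum for any d ≥ 0.

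Multiplying effect and SE by 1.29 to reach the MDS-UPDRS scale leaves d/SE unchanged.

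**Step 3: vary the number contributing.** The 0.228 assumes that everyone supplies wash-out data. As an assumption, let the share run from 100% down to 22%. The lower values come from the one-third not yet on dopaminergic therapy (SAP 3.6) and from 100 − 70 − 8 = 22% (SAP 3.8).

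| Share contributing | n per arm | SE | Supplied rule flags 0.65 | Protocol rule flags 0.65 |
|---|---|---|---|---|
| 100% | 135 | 0.228 | 0.0000008 | 0.81 |
| 50% | 67.5 | 0.323 | 0.00004 | 0.52 |
| 33% | 45 | 0.395 | 0.0002 | 0.38 |
| 22% | 29.7 | 0.486 | 0.0005 | 0.27 |

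**Step 4: follow the case into the fallback.** Read the absence test in the true symptomatic direction on the MDS-UPDRS scale. With everyone contributing, SE = 1.29 × 0.228 = 0.294 and d = 1.29 × 0.65 = 0.839. Absence is declared if the estimate is below 2.1 − 1.645 × 0.294 = 1.616.

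- Supplied rule: almost nothing is flagged first, so P(declared absent) = Φ((1.616 − 0.839)/0.294) = 0.996.
- Protocol rule: estimates above 1.96 × 0.294 = 0.577 are flagged first, so P(declared absent) = Φ((0.577 − 0.839)/0.294) = 0.19.

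At 33% contributing the pair is 0.80 against 0.62. At 22% there is no material difference.

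**Step 5: compare the sentences.** Removing one unbroken run of five words from the protocol sentence gives the supplied SAP sentence exactly. That run lies between the two places where slopes are mentioned, so a skip from one to the other produces it. In SAP 6.6.1 the sentence on the shared baseline has lost its verb and taken in a covariate phrase. In SAP 6.6.9 the last sentence repeats words from the one before and resumes in mid-word. Protocol 10.5.1 and 10.5.9 carry intact versions of both.

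**The case against.** The strongest objection is that the plan may contain no error at all. A skip between two matching phrases leaves grammatical text by construction, so the fact that the sentence reads well proves little. The two garbled sentences elsewhere in SAP 6.6 also break at repeated words. No passage gives a reason for reversing the direction or dropping wash-in, and SAP 6.8.7 still treats 6.6.8 as covering wash-in. This stands, and it lowers confidence. It does not clear the sentence: an author copying from the protocol can make the same slip, and the paragraph was edited for early closeout, since it now has "slope from 24 to 27 months (or from V10-equivalent visit on study drug to SV". That edit is in another sentence and says nothing about the presence rule. The supplied text cannot settle the matter.

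A reader might infer that a withdrawal effect of any size goes untested. The documents do not support that. The fallback still tests against 2.1 points/month, and if it is read in the true direction, a worsening near or above that bound would generally not be declared absent. The gap is for smaller effects such as 0.65.

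A fair criticism of Step 3 is that the 22% and 33% shares assume scores after dopaminergic therapy are excluded. SAP 6.6.8 does not say so, and SAP 3.2 also plans an analysis adjusted for levodopa equivalent dosage. The contrast between the two rules does not depend on that choice.

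**Conclusion.** The concern holds conditionally, with low to medium confidence. As supplied, the presence rule in SAP 6.6.8 is reversed and omits wash-in, and following it would give the wrong inference. At the SAP's design effect it would flag a true wash-out worsening with probability below 0.000001, against 0.81 under the protocol rule. Across the assumed range of contributors it never exceeds 0.0005. These figures rest on the normal approximation and on applying the wash-in standard error to wash-out, as SAP 3.9 does. No power figure applies at wash-in, because no presence test is stated.

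Two stronger readings should be resisted. One is that the direction was changed deliberately; nothing in the documents indicates that. The other is that the main conclusions are compromised: the primary test (SAP 6.6.1) and the three-part disease-modification test (SAP 6.6.9) take no input from 6.6.8. The damage is confined to the supporting statement about symptomatic effects.

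One smaller gap remains whatever the source page shows. The absence test names no period, in the SAP or in the protocol, and its direction is unclear if the presence rule really is reversed.

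**What to change.** 1. Check the source SAP page for section 6.6.8.
2. If it reads as supplied, restore the protocol's clause: "Significantly smaller slopes during wash-in or larger slopes during wash-out among subjects treated with inosine".
3. In either case, state that the 2.1 points/month absence test applies to each period in its own symptomatic direction: a smaller slope on inosine at wash-in, a larger one at wash-out.

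If the source page already has the clause, the presence rule needs no change and only step 3 remains. The cost is one page check and at most two clauses of wording before the blind is broken. No new data or new model is needed, and the primary test does not change.
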